## 4.3 General Considerations

### 4.3.1 Missing Data

In general, other than for partial dates, missing safety data will not be imputed and will be treated as missing. However, in all data presentations (except listings), safety assessment values below the limit of quantitation (BLQ) will be imputed as ‘lower limit of quantitation (LLQ)’, where LLQ will be replaced with the value for the lower limit of quantitation. In listings, BLQ values will be reported as ‘<LLQ’.

#### 4.3.1.1 Imputation of Partial Dates

For missing medication and AE start dates, the following will be applied:

- If year is missing (or completely missing), no imputation will be performed.
- If year is present but months and day are missing, or year and day are present but month is missing, the missing day/month will be imputed as 01 January.
- If year and month are present but day is missing, the missing day will be imputed as first day of the month.

For missing medications and AE end dates, the following will be applied:

- If year is missing (or completely missing), no imputation will be performed.
- If year is present but month and day are missing, or year and day are present but month is missing, the missing day/month will be imputed as 31 December.
- If year and month are present but day is missing, the missing day will be imputed as last day of the month.
- If a subject dies in the same month/year of partial stop date, the date of death will be used.

In addition, for AEs, if for a partial start date, the AE start date could (when also considering the AE end date) potentially be on the first dose of study intervention date, the AE start date will be imputed with the first dose of study intervention date to assume a “worst case” scenario; e.g. AE from UNK-Jun-2017 to 23-Jul-2017 with the first dose of study intervention date 21-Jun-2017, then the AE start date will be imputed to 21-Jun-2017.

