#### 4.3.2 Standard Dictionaries for Coding

The following dictionaries will be used to code medical verbatim terms for the clinical data below.

Types of Data	Coding Tools and Latest Version
Adverse events	Medical Dictionary for Regulatory Activities (MedDRA) Version 24.0
Prior and concomitant medications	World Health Organization Drug Dictionary (WHODrug) March 2021
Prior systemic therapies	WHODrug March 2021
Subsequent anticancer therapies	WHODrug March 2021
Medical history	MedDRA Version 24.0

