#### 4.10.2 Primary Efficacy Variable – ORR

The ORR (proportion of subjects achieving a CR or PR using the number of subjects in the mITT analysis set as the denominator) will be estimated, along with the 2-sided 95% exact CI using the Clopper-Pearson exact method for binomial proportions. Responses for the primary ORR analysis will be assessed using the 2007 revised IWG criteria (Cheson 2007). Missing data will be imputed by assuming that any subjects not exhibiting a response (CR or PR) are non-responders. Responses occurring after the start of subsequent anticancer therapy will not be included in the numerator.

The primary analysis of ORR will be performed 12 months after the last subject is randomized, using the time windows specified in [Section 4.2](#) as applicable.

A by-subject listing of the primary efficacy data will be provided.

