#### 4.10.3 Secondary Efficacy Variables

The secondary efficacy analyses will be conducted on the mITT analysis set.

- ORR according to 2014 Lugano criteria (Cheson 2014) will be analyzed in the same fashion as the primary endpoint

*Note: with the exception of TTF, all additional secondary response endpoints (described below) as well as PFS will be assessed separately using 2007 revised IWG criteria (Cheson 2007) and 2014 Lugano criteria (Cheson 2014)*

- ORR, at 6, 12, 18, and 24 months after first dose of study intervention, defined as the proportion of subjects achieving CR or PR at each of these time points.
- PFS will be assessed using KM methods from time of first dose of study intervention to PD or death. Median PFS will be estimated, along with the 95% CI. The 6-month and 12-month PFS estimates will also be presented. See Table 1 for event and censoring definitions. Kaplan-Meier survival curves by arm will be produced.
- TTF will be calculated as the time from first dose of study intervention until discontinuation for any reason and will be summarized using KM methods. Median TTF will be estimated, along with the 95% CI. The 6-month and 12-month TTF estimates will also be presented. Subjects who are still on treatment at time of data cutoff will be censored at their last dose date. Kaplan-Meier survival curves by arm will be produced.
- DOR will be calculated for those subjects with a CR or PR from the time of first response to PD using KM methods. Median DOR will be estimated, along with the 95% CI. The 6-month and 12-month DOR estimates will also be presented. See Table 1 for event and censoring definitions. Kaplan-Meier survival curves by arm will be produced.
- OS will be assessed using KM methods from time of first dose of study intervention to death. Median OS will be estimated, along with the 95% CI. The 6-month and 12-month OS estimates will also be presented. Subjects without documented death will be censored at their last known alive date. Kaplan-Meier survival curves by arm will be produced.
- LNRR will be calculated as the proportion of subjects achieving  $\geq 50\%$  decrease in the sum of the product of the diameters of target lymph nodes. A 2-sided 95% exact CI for LNRR will also be estimated. A waterfall plot of minimum percent change in the sum of the product of the diameters by arm will be produced.

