**Table 1: Primary PFS Censoring/Event Rule**

Situation	Date of Event or Censoring	Outcome
No adequate baseline disease status assessment	Date of randomization + 1 day	Censored

No adequate post-baseline disease status assessment unless death occurs prior to first scheduled post-baseline assessment	Date of randomization + 1 day	Censored
No documented progression or death	Date of last adequate disease status assessment	Censored
Documented progression with $\leq 1$ missing scheduled disease status assessment before progression	Date of the earliest assessment that results in a finding of unequivocal progression	Event
Death before progression being documented with $\leq 1$ missing scheduled disease status assessment before death	Date of death	Event
Documented progression or death following a gap between adequate disease status assessments equivalent to 2 missed visits	Date of last adequate disease status assessment before the gap	Censored
New anticancer treatment or procedure started before documented progression	Date of last adequate disease status assessment prior to start of new anticancer therapy	Censored

Note: Disease status assessment includes radiologic documentation (CT, PET/CT, MRI scans) (chest, abdomen and pelvis, others as clinically indicated), bone marrow biopsy/aspirate (may not be required of all patients at all scheduled disease status assessments), and focused physical examination (disease related symptoms, liver and spleen assessment). An adequate baseline disease assessment is any assessment with measurable target lesions from scans. An adequate post-baseline disease status assessment is any disease status assessment for which a disease status of CR, PR, SD or PD is arrived per revised International Working Group (IWG) response criteria for malignant lymphoma.

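### SAP 4.3.1.1 dates partly recorded medication starts as early as possible and has no separate rule for subsequent anticancer therapy, so a progression followed by new therapy in the same month can become an earlier PFS or DOR censoring

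*SAP*

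**What the plan says.** SAP 4.3.1.1 opens its start-date rule with "For missing medication and AE start dates, the following will be applied". Three steps follow. With the year missing, nothing is imputed. With the month missing, "the missing day/month will be imputed as 01 January". With only the day missing, "If year and month are present but day is missing, the missing day will be imputed as first day of the month". The one adjustment tied to dosing dates is for adverse events. Medications have no lower bound at first dose, last dose, progression or response.

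The start of new anticancer therapy is used in two efficacy rules:

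- **PFS and DOR.** SAP Table 1 has a row for "New anticancer treatment or procedure started before documented progression". The outcome is censoring, dated at "Date of last adequate disease status assessment prior to start of new anticancer therapy". SAP 4.10.3 sends both PFS and DOR to this table: "See Table 1 for event and censoring definitions".
- **ORR.** SAP 4.10.2: "Responses occurring after the start of subsequent anticancer therapy will not be included in the numerator".

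SAP 4.3.2 lists "Subsequent anticancer therapies" as its own data type, coded in WHODrug, apart from prior and concomitant medications. No section gives a partial-date rule for it. SAP 4.8 does use the word medications for agents started more than 30 days after the last dose, which it labels post-treatment.

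**The concern.** Taking the earliest possible date is cautious when the question is whether an adverse event was treatment-emergent or a drug concomitant. It is not cautious when the question is which came first, progression or the next therapy. Progression commonly prompts the next therapy within weeks, so the two often share a calendar month, and an imputed 1st of the month then falls before the progression. Table 1 treats the subject as having started therapy before progressing and drops the event.

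The resulting censoring is informative, because these subjects are censored as a consequence of having progressed. PFS and DOR, under both the 2007 IWG and the Lugano criteria, would tend to look longer than they are.

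For the ORR the same mechanism could remove a genuine responder, which would lower the estimate.

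**Working it through.** **1. How far back the censoring goes.** Cycle 1 lasts 70 days and later cycles 28 days, with scans at Day 1 of Cycles 2, 4, 6, 9, 13 and 17 (SAP 3.1).

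| Scan | Study day | Days since previous scan |
|---|---|---|
| C2D1 | 71 | – |
| C4D1 | 127 | 56 |
| C6D1 | 183 | 56 |
| C9D1 | 267 | 84 |
| C13D1 | 379 | 112 |
| C17D1 | 491 | 112 |

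Worked case: first dose 1 March 2021, stable disease at C2D1 on 10 May (Day 71), progression at C4D1 on 5 July (Day 127). New therapy starts on 20 July and is recorded as July 2021 with no day. It is imputed to 1 July, and the event at Day 127 becomes a censoring at Day 71. A progression at C13D1 would go back to C9D1: 379 − 267 = 112 days.

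**2. How often a partial date reverses the order.** The rule was applied to every calendar day of 2020–2023, with the true therapy start set a fixed gap after the progression or response. The table shows the share of partial dates imputed to before that event.

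| True gap (days) | Day missing | Month missing |
|---|---|---|
| 7 | 74% | 98% |
| 14 | 51% | 96% |
| 21 | 28% | 94% |
| 28 | 5% | 92% |
| 35 | 0% | 90% |
| 180 | 0% | 50% |

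**3. PFS events lost per arm.** Three inputs are assumptions, since the documents give none: 30 progressors per arm who go on to new therapy, 10% of start days missing, and a uniform lag of 7–28 or 7–35 days. With progression uniform over a 30.4-day month, P(same month | lag L) = 1 − L/30.4 for L < 30.4, and 0 otherwise.

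- Lag 7–28: mean 17.5, so 1 − 17.5/30.4 = 0.42.
- Lag 7–35: (30.4 − 7)² / (2 × 30.4 × 28) = 547.6/1702.4 = 0.32.
- Events lost: 30 × 0.10 × 0.32 = 1.0 to 30 × 0.10 × 0.42 = 1.3.
- Range over the missing-day rate: 5% gives 0.5–0.6; 20% gives 1.9–2.5.

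As a share of these progressors, 10% missing gives 0.10 × 0.32 to 0.10 × 0.42, about 3% to 4%. These figures slightly overstate the effect, because a progression on the 1st is not preceded by its imputed date.

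**4. ORR.** The plan's design figures reproduce. With 6/15 treated as binding and 22/51 as the final threshold, sum over x = 6 to 15 of Bin(x; 15, p) × P[Bin(36, p) ≥ 22 − x]. At p = 0.30 this gives 0.0246 (stated 0.025), and at p = 0.55 it gives 0.9035 (stated 90%).

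If a share m of true responders were struck (m is assumed), p is replaced by p(1 − m):

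| m | Type I error | Power |
|---|---|---|
| 0 | 0.0246 | 0.904 |
| 1% | 0.0220 | 0.893 |
| 2% | 0.0196 | 0.882 |
| 4% | 0.0155 | 0.858 |

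Both columns fall, so the error is conservative. With only the day missing, a subject is struck only if the first response falls in the same month as the new therapy, because a response before that month still counts. The other route is a therapy date known only to the year.

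**The case against.** The strongest objection is scope. SAP 4.3.1 opens with missing safety data, 4.3.1.1 pairs medications with adverse events, and 4.3.2 lists subsequent anticancer therapy apart from prior and concomitant medications. SAP 4.10.1.3 says efficacy data are not imputed unless a method is given. Table 1 also covers new procedures, which 4.3.1.1 does not mention. This stands in part: applying 4.3.1.1 to these dates is an inference, supported by the wording of SAP 4.8 but not explicit. It does not close the gap. If 4.3.1.1 does not apply, nothing does, and Table 1 cannot order a progression and a partly dated therapy in the same month. The SAP tailors partial-date rules to purpose for treatment-emergent events, concomitant medication and diagnosis date, but not for this one.

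It is also fair that PFS and DOR are secondary and descriptive, with no formal testing and no formal comparison between arms (Protocol 9.4.1), and that every input to the count of lost events is assumed.

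A reader might infer that the primary ORR is at material risk, since 22/51 meets the final rule and 21/51 does not. The documents do not support that. The ORR routes are narrow, and Protocol 6.6 asks for start and end dates of medication received during the study. The 22/51 threshold only prompts consideration within a totality-of-data judgement (Protocol 9.2, SAP 4.13). At 22/51 the exact lower 95% limit is 29.3%, so that count does not itself exclude 30%; 23/51 does, at 31.1%.

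A reader might also infer that imputed dates would often precede progression across the trial. That is true only among partial dates with a short gap; across progressors it is about 3% to 4% under the assumptions above.

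**Conclusion.** The point holds for PFS and DOR. Applied as written, a stated rule turns a true progression into a censoring one scan interval earlier, by 56 to 112 days, whenever new therapy follows in the same month, its start day is unrecorded and the progression was not on the 1st. The direction is towards longer PFS and DOR. The size is probably small, about one event per arm, and rests on three assumed inputs: 30 progressors on new therapy, 10% missing days, and a lag of 7–28 or 7–35 days. The actual rate of partial dates is not in the documents.

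For the primary ORR the effect should be rare and conservative, and it does not threaten the primary conclusion. That 4.3.1.1 reaches subsequent anticancer therapy is the natural reading but not a certain one; on the other reading the SAP has no rule at all. The correction is the same either way and is worth making before database lock, because in an open-label trial event status should not be settled after outcomes are seen.

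**What to change.** State in SAP 4.3.1.1 that its rules do not apply to subsequent anticancer therapy, and add a separate rule:

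- If the known part of the date is compatible with a start after documented progression (or, for ORR, after first response), place the start on the day after that event, or on the first day of the known period if that is later.
- Otherwise use the later of the first day of the known period and the day after the last duvelisib dose.
- Never impute a date outside the known month or year.
- Do not apply the last-dose bound to anticancer therapy recorded as given during study treatment. SAP 4.5 foresees such cases under the per-protocol set, and moving them to after dosing would count responses that 4.10.2 excludes.
- Repeat PFS, DOR and ORR with the earliest possible date as a sensitivity analysis.

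A last-dose bound alone would not be enough. Scans fall from Day −7 to Day 1 of a cycle and Weeks 1 and 2 of later cycles are a planned holiday, so the last dose can precede the scan that shows progression.

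The cost is one SAP paragraph and a few lines of derivation code, with no change to sample size, type I error or power. The downside is a small risk of counting as an event a progression that truly followed new therapy; the sensitivity analysis would show how much that matters.

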#### 4.3.1.2 Handling Missing Dates/Months/Years for Determination of TEAEs

Adverse events (AEs) with incomplete onset dates will be handled as follows for the purpose of determining treatment emergence according to the definition provided in [Section 4.11.2](#).

- If the start/end date of an AE is partially missing, the date will be compared as accurately as possible with the first dose of study drug and the date of last dose of study drug plus 30 days. The AE will be assumed to be treatment emergent if it cannot be definitively shown that the AE did not start or worsen during the treatment-emergent period.
- If the start date is completely missing, an AE will be considered treatment-emergent unless the stop date is before first dose of study drug.

The original partial or missing date will be displayed in the AE listings.

#### 4.3.1.3 Handling Missing Dates/Months/Years for Concomitant Medications

Prior or concomitant medications with incomplete start dates will be handled as follows for the purpose of determining whether a non-study medication is a concomitant medication

- If the start/stop date of a medication is partially missing, the date will be compared as accurately as possible with the first dose date of study drug and the last dose date of study drug plus 30 days. The medication will be assumed to be concomitant if it cannot be definitively shown that the stop date is before first dose date of study drug, or the start date is more than 30 days after the last dose date of study drug.
- If the start/stop dates are completely missing, a medication will be considered concomitant.

#### 4.3.1.4 Handling Missing Dates/Months/Years for Disease History

For the purpose of calculating the duration from initial diagnosis, partial/missing dates for diagnosis will be imputed as follows:

- If both day and month are missing and the year is prior to the year of screening, the imputed date will be 01 July
- If both day and month are missing and year is the same as the year of screening, the imputed date will be the middle point between 01 January of the year and the screening date. If the middle point falls between two dates, the first of the two dates will be used.
- If day is missing and the month and year are prior to the month and year of screening, the imputed date will be the 15th day of the month.
- If day is missing and the month and year are the same as the month and year of screening, the imputed date will be the middle point between the first day of the month and the screening date. If the middle point falls between two dates, the first of the two dates will be used.
- No imputation will be performed if the year is missing.

#### 4.3.2 Standard Dictionaries for Coding

The following dictionaries will be used to code medical verbatim terms for the clinical data below.

Types of Data	Coding Tools and Latest Version
Adverse events	Medical Dictionary for Regulatory Activities (MedDRA) Version 24.0
Prior and concomitant medications	World Health Organization Drug Dictionary (WHODrug) March 2021
Prior systemic therapies	WHODrug March 2021
Subsequent anticancer therapies	WHODrug March 2021
Medical history	MedDRA Version 24.0

#### 4.4 Software

All report outputs will be produced using [SAS® version 9.3](#) or a later version in a secure and validated environment.

#### 4.5 Analysis Sets

##### Modified Intent-to-treat (mITT) Analysis Set

The modified intent-to-treat (mITT) analysis set will include all subjects who receive at least one dose of study drug. The mITT analysis set will serve as the primary analysis set for all efficacy endpoints and baseline characteristics.

##### All-treated (AT) Analysis Set

The all-treated (AT) analysis set will include all subjects who received at least one dose of study drug. The AT analysis set will be the primary analysis set for all safety endpoints.

##### Per-protocol (PP) Analysis Set

The per-protocol (PP) analysis set includes all subjects in the mITT analysis set who do not violate the protocol in a way that would significantly affect the study outcome. Subjects who meet any of the following criteria may be excluded from the PP analysis set:

- Do not have histologically confirmed diagnosis of iNHL: FL Grades 1 to 3a, marginal zone lymphoma (MZL; splenic, nodal, or extranodal), or SLL
- Have not received at least 1 prior systemic regimen for iNHL
- Must have at least one bi-dimensionally measurable lesion  $\geq 1.5$  cm (which has not been previously irradiated) according to 2007 revised IWG response criteria (Cheson 2007)

- Clinical or histological evidence of transformation to a more aggressive subtype of lymphoma or Grade 3b FL or Richter's transformation or CLL
- Never received study drug
- Received concomitant anticancer therapy prior to observation of ORR

Subjects with major protocol deviations not listed above and with COVID-19 related protocol deviations will be considered for removal from the PP analysis set on a case by case basis. The PP analysis set will be a secondary analysis set for the analysis of ORR. Final determination of subjects to be included in the PP analysis set will be determined prior to database lock and unblinding of treatment assignment.

## 4.6 Study Subjects

### 4.6.1 Disposition of Subjects

A clear accounting of the disposition of all subjects who enroll in the study will be provided, from screening to study completion.

The disposition of subjects will include the number and percentage of subjects for the following categories: the number randomized, the number and percentage randomized but not dosed, and the number and percentage dosed. These categories will be summarized for each treatment arm and for the two treatment arms combined (total). The percentages will be based on all randomized subjects. An end-of-treatment disposition (still on treatment vs. discontinued from treatment) will be provided for each treatment arm and for the two treatment arms combined (total) based on the AT analysis set. The primary reason for discontinuation will be included in the table. A listing of these subjects will also be provided, broken down by center and treatment arm.

An end-of-study disposition (still on study vs. discontinued from study) will also be provided for each treatment arm and for the two treatment arms combined (total) based on the mITT analysis set. The primary reason for study discontinuation will be included in the table. A listing of these subjects will also be provided, broken down by center and treatment arm.

A summary of strata as captured in IRT will be presented by treatment arm and for the two treatment arms combined (total) based on the mITT analysis set. A summary table and a listing of discrepancies in data for stratification factors between those captured in the IRT and those reported on the eCRF will be presented. Both the summary table and listing will be displayed by treatment arm.

All subjects in the mITT population will also be summarized by site and by country.

Upon database release, protocol deviation and analysis set outputs will be produced and will be sent to Secura Bio for review. An analysis set classification meeting will be arranged to discuss the outputs and to decide which subjects and/or subject data will be excluded from certain

analyses. Decisions made regarding the exclusion of subjects and/or subject data from analyses will be made prior to unblinding and will be documented and approved by Verastem.

The following analysis set summaries will be prepared:

- The number and percentage of subjects entering and completing each phase of the study by treatment group and overall for each analysis set (Analysis set: mITT).
- A by-subject listing of analysis set details presented by treatment group that will include: center, subject identifier, inclusion/exclusion flag for each set and reason for exclusion from each set. All subjects screened should appear on this listing.

